5.1 Disease Related Criteria

- a. Patients must have histologically or cytologically confirmed Stage IV (AJCC 7th Edition) or recurrent non-small cell lung cancer (NSCLC).
- b. Patients must have documented presence of an EGFR exon 19 deletion or exon 21 (L858R) substitution mutation. T790M mutation or other molecular abnormality will be allowed as long as it accompanies one of the mutations listed above. EGFR testing must have been performed using a FDA-approved test or in a CLIA-certified laboratory.
- c. Patients must have tissue available and must agree to submission of tissue and blood as outlined in [Section 15.0](#). One to two paraffin-embedded tissue blocks or 15-20 unstained slides are requested (a minimum of 12 slides is required).

Cytology (i.e. fine-needle aspirations, pleural effusion specimens) is acceptable if a cell block or sufficient unstained slides are available. Tumor material must be reviewed by a local pathologist who must confirm that at least 100 viable tumor cells are present in the sample and sign the **S1403** Pathology Review Form prior to registration. Patients must also be willing to submit blood samples for correlative research at baseline, during treatment and at progression.

- d. Patients enrolled at sites participating in the Repeat Biopsy Study must agree to submission of tissue obtained by a repeat biopsy performed at the time of disease progression.
- e. Patients must not have received any prior systemic anticancer therapy for advanced or metastatic disease including chemotherapy or EGFR tyrosine kinase inhibitor therapy (including gefitinib, erlotinib, afatinib, or any experimental EGFR TKI agents). Prior chemotherapy for non-metastatic disease (i.e. adjuvant therapy or concurrent chemo-radiotherapy) is allowed as long as >12 months has passed since completion of therapy. Adjuvant EGFR-directed therapy is not allowed. Local therapy (i.e. palliative radiotherapy) is allowed as long as a period of 7 days has passed since the last dose was received and the patient has recovered from any associated toxicity at the time of registration.
- f. Patients may have measurable or non-measurable disease (see [Section 10.1](#)) documented by CT or MRI within 42 days prior to registration. The CT from a combined PET/CT may be used only if it is of diagnostic quality as defined in [Section 10.1a](#). Laboratory parameters are not acceptable as the only evidence of disease. In order to qualify as measurable per [Section 10.1a](#), measurable disease must be outside previous radiation field. All disease must be assessed and documented on the Baseline Tumor Assessment Form (RECIST 1.1).
- g. Patients must have a CT or MRI scan of the brain to evaluate for CNS disease within 42 days prior to registration. Patient must not have symptomatic brain metastases or evidence of leptomeningeal carcinomatosis. Patients with asymptomatic brain metastases are eligible if off of steroids for at least 7 days prior to registration without development of symptoms.

5.2 Clinical/Laboratory Criteria

- a. Patients must have adequate bone marrow function as evidenced by all of the following: ANC \geq 1,500/mcL; platelets \geq 75,000/mcL; and hemoglobin \geq 9 g/dL. These results must be obtained within 28 days prior to registration.
- b. Patients must have adequate liver function as evidenced by the following: total bilirubin \leq 1.5 x institutional upper limit of normal (IULN), and AST and ALT \leq 2.5 x IULN (or \leq 5 x IULN for patients with known liver metastases). These results must be obtained within 28 days prior to registration.
- c. Patient must have adequate renal function as evidenced by ONE of the following: serum creatinine \leq 1.5 x IULN OR measured or calculated creatinine clearance \geq 60 mL/min. This result must have been obtained within 28 days prior to registration.

$$\text{Estimated creatinine clearance} = \frac{(140 - \text{age}) \times \text{wt (kg)} \times 0.85 \text{ (if female)}}{72 \times \text{creatinine (mg/dl)}}$$

- d. Patients must not have significant gastrointestinal disorders with diarrhea as a major symptom (e.g. Crohn's disease, malabsorption, etc).
- e. Patients must be able to swallow medication by oral route.
- f. Patients must not have a history of clinically relevant cardiovascular abnormalities such as uncontrolled hypertension, congestive heart failure NYHA classification of 3 (see [Section 18.5](#)), unstable angina or poorly controlled arrhythmia or myocardial infarction [New York Heart Association Criteria](#) within 6 months prior to registration. If clinically indicated, echocardiogram or MUGA must be performed and cardiac ejection fraction must be $\geq 50\%$
- g. Patients must not have had major surgery within 28 days prior to registration or be scheduled for surgery during the projected course of protocol treatment. Tumor biopsy is allowed.
- h. Patients must not have a known history of active hepatitis B infection (defined as presence of Hep B sAg and/ or Hep B DNA), active hepatitis C infection (defined as presence of Hep C RNA) and/or known HIV seropositive.
- i. Patients must not have any other concomitant serious illness or organ system dysfunction which in the opinion of the investigator would either compromise patient safety or interfere with the evaluation of the safety of the study drug.
- j. Patients must not be planning to receive any other investigational agents during the course of protocol treatment.
- k. Patients must not have a history of allergic reactions attributed to compounds of similar chemical or biologic composition to afatinib and/or cetuximab.
- l. Prestudy history and physical must be obtained with 28 days prior to registration.
- m. Patients must have Zubrod Performance Status of 0 - 2 (see [Section 10.4](#)).
- n. No other prior malignancy is allowed except for the following: adequately treated basal cell or squamous cell skin cancer, *in situ* cervical cancer, adequately treated Stage I or II cancer from which the patient is currently in complete remission, or any other cancer from which the patient has been disease free for three years.
- o. Patients must not be pregnant or nursing because of the risk of fetal harm including fetal death. Women/men of reproductive potential must have agreed to use an effective contraceptive method. A woman is considered to be of "reproductive potential" if she has had menses at any time in the preceding 12 consecutive months. In addition to routine contraceptive methods, "effective contraception" also includes heterosexual celibacy and surgery intended to prevent pregnancy (or with a side-effect of pregnancy prevention) defined as a hysterectomy, bilateral oophorectomy or bilateral tubal ligation. However, if at any point a previously celibate patient chooses to become heterosexually active during the time period for use of contraceptive measures outlined in the protocol, he/she is responsible for beginning contraceptive measures.

5.3 Regulatory Criteria

- a. *Patients must be informed of the investigational nature of this study and must sign and give written informed consent in accordance with institutional and federal guidelines.*
- b. As a part of the OPEN registration process (see [Section 13.4](#) for OPEN access instructions) the treating institution's identity is provided in order to ensure that the current (within 365 days) date of institutional review board approval for this study has been entered in the system.

6.0 STRATIFICATION FACTORS

Patients will be randomized between Arm 1 (afatinib and cetuximab) and Arm 2 (afatinib) using a dynamic balancing algorithm. (24)

Stratification is based on performance status (0-1 vs 2) and EGFR mutation type (exon 19 deletion versus L858R mutation).

7.1 Pre-Medication

All patients who will receive cetuximab will be premedicated with:

Agent	Dose	Route	Duration
Diphenhydramine	50mg	IV	prior to the first dose of cetuximab hydrochloride

Diphenhydramine must be given prior to the first dose of cetuximab in an effort to prevent a hypersensitivity reaction. Premedication is recommended prior to subsequent doses, but at the treating physician's discretion, the dose of diphenhydramine may be reduced.

Consideration may be given to administering magnesium sulfate 2g IV prior to cetuximab infusion in an effort to prevent hypomagnesemia.

7.2 Treatment

Patients will be randomized to Arm 1 or Arm 2.

a. Arm 1

Agent	Dose	Route	Day	Schedule*
Afatinib	40 mg	PO	1-28	Daily**
Cetuximab	500 mg/m ²	2 hour IV infusion	1 and 15	q 28 days

* Note: One cycle = 28 days.

** Afatinib must not be taken with food. Take on an empty stomach at least 1 hour before or 2 hours after a meal. Do not take a missed dose within 12 hours of the next dose.

Treatment will continue as above until one of the criteria in [Section 7.6](#) is met.

b. Arm 2

Agent	Dose	Route	Day	Schedule*
Afatinib	40 mg	PO	1-28	Daily**

* Note: One cycle = 28 days.

** Afatinib must not be taken with food. Take on an empty stomach at least 1 hour before or 2 hours after a meal. Do not take a missed dose within 12 hours of the next dose.

Treatment will continue as above until one of the criteria in [Section 7.6](#) is met.

7.3 Drug Compliance Documentation

The study medication will be given in accordance with the protocol and the instructions of a site investigator. The appropriate number of afatinib tablets for 4 weeks of treatment will be provided to patients to be self-administered at home. Patients will be asked to bring the remaining trial medication at the end of each visit to the investigator site for a compliance check. The remaining film-coated tablets will be counted by the investigator/site staff and recorded at the investigator site. Discrepancies between the number of tablets remaining and the calculated number of tablets the patients should have taken must be documented and explained. At the end of each 4 week period, any remaining medication will be collected. If the patient is eligible for further treatment, a new bottle of study medication must be dispensed.

The investigator can withdraw a patient from the study in the event of serious and persistent non-compliance which jeopardizes the patient's safety or render study results for this patient unacceptable. Patients who do not attend a minimum of 75% of scheduled study visits, unless due to exceptional circumstances, should be evaluated for compliance.

Drug compliance will be recorded by patients in the Intake Calendar (see [Section 18.2](#)). Institutional CRAs will review and ascertain patient adherence with protocol therapy at the end of treatment for each cycle. Calendar should be kept in the patient's clinic chart. Note that the Intake Calendar is provided only as a tool for tracking patient compliance. Sites may utilize institutional pill diaries or other source documentation in place of the Intake Calendar at the discretion of the treating physician.

7.4 Concomitant medications or therapy

a. Concomitant medication

Afatinib is a substrate of P-gp and the use of Ps-gp inhibitors or inducers should be avoided. Common medications that should be avoided are reported below.

Inhibitors	Inducers
Amiodarone	Carbamazepine
Azithromycin	Phenytoin
Captopril	Rifampicin
Carvedilol	St John's Wort
Clarithromycin	Phenobarbital Salt
Conivaptan	Tipranavir
Cyclosporine	Ritonavir
Diltiazem	
Dronedarone	
Erythromycin	
Felodipine	
Itraconazole	
Ketoconazole	
Lopinavir	
Nelfinavir	
Ritonavir	
Quinidine	
Ranolazine	
Saquinavir	
Tacrolimus	
Ticagrelor	
Verapamil	

Prior to initiation of therapy, patients should be informed that they may experience diarrhea, and consideration may be given to providing patients prophylactic anti-diarrheal medication. One example of a prophylactic regimen is the following:

Loperamide 4 mg with the first dose of afatinib, followed by 2 mg every 4 hours for the first 3 days. After the first 3 days, take loperamide 2 mg every 6-8 hours until the end of the first cycle of therapy whether the patient is experiencing diarrhea or not. Beyond the first cycle it may be continued at the discretion of the treating physician. Loperamide should be held if constipation develops.

b. Radiotherapy

After study enrollment, palliative radiotherapy may be given for bone pain or for other reasons (e.g. bronchial obstruction, skin lesions), provided that the total dose delivered is in a palliative range according to institutional standards. The irradiated area cannot be used for tumor response assessment. During palliative radiotherapy, protocol treatment should be held and may be resumed once the

patient has recovered from any radiation associated toxicity. Continuous interruption of >28 days due to palliative radiotherapy will not be allowed; in such a circumstance the patient must be removed from protocol treatment.

c. **Surgery**

In case of major surgery (as judged by the investigator), it is recommended to stop treatment with afatinib and cetuximab around one week prior to the surgery, and to restart treatment after complete wound healing. If afatinib or cetuximab is interrupted for more than 28 days, the patient must be removed from protocol treatment.

d. **Tumor biopsy**

At select institutions, patients will be required to undergo a repeat tumor biopsy at the time of disease progression following an initial response. Repeat biopsies will be obtained **only** from patients who have disease progression after one of the following treatment responses:

- Objective response (complete or partial response), or
- Stable disease \geq 6 months.

The biopsy site should be chosen based on safety and the presence of tumor growth at that site. Afatinib and cetuximab do not need to be held around the time of the biopsy. See [Section 15.5](#) and [15.6](#) for more details.

7.5 Emergency Procedures

Cetuximab: Allergic reactions may occur during or following cetuximab administration. As a routine precaution, patients enrolled in this study will be observed closely for any potential adverse events by the medical staff from the start of the cetuximab infusion to one hour after the end of the infusion in an area with resuscitation equipment and other agents (epinephrine, prednisone equivalents, etc.) available. Vital signs (blood pressure, heart rate, respiratory rate and temperature) should be checked prior to the administration, midway through the infusion, at the completion of the infusion and 1 hour post the infusion. Should an allergic or infusion reaction to cetuximab occur, the patient must be treated according to the best available medical practices. The cetuximab infusion rate should never exceed 5 mL/minute. Epinephrine and diphenhydramine for injection should be readily available during the infusion, for emergency treatment of hypersensitivity reactions. See [Section 8.3c](#) for additional details.

Afatinib: Rescue medications to reverse the actions of afatinib are not available. There is no specific antidote for overdosage with afatinib. Potential adverse events should be treated symptomatically. Common adverse events of treatment with afatinib with specified management recommendations and/or requirements include diarrhea, nausea, rash/acne, and mucositis/stomatitis. To improve tolerability and the probability of clinical benefit, patients should receive prompt and appropriate supportive care at the first signs of symptoms. See [Section 8.0](#) for details.

Careful assessment of all patients with an acute onset and/or unexplained worsening of pulmonary symptoms (dyspnea, cough, fever) should be performed to exclude interstitial lung disease (ILD). Study drugs should be interrupted pending investigation of these symptoms. If interstitial lung disease is diagnosed, study drug must be permanently discontinued and appropriate treatment instituted as necessary.

Patients who present with symptoms of keratitis, such as acute or worsening eye inflammation, lacrimation, light sensitivity, blurred vision, eye pain and/or red eye should be referred promptly to an ophthalmic specialist. If a diagnosis of ulcerative keratitis is

confirmed, treatment with afatinib should be interrupted or discontinued. If keratitis is diagnosed, the benefits and risks of continuing treatment with afatinib should be carefully considered. Afatinib should be used with caution in patients with a history of keratitis, ulcerative keratitis or severe dry eye. Contact lens use is a risk factor for keratitis and ulceration

7.6 Criteria for Removal from Protocol Treatment

- a. Unequivocal progression of disease or symptomatic deterioration (as defined in [Section 10.2e](#)). Patients may continue to receive study treatment after radiographic progression per RECIST 1.1 as long as they continue to experience clinical benefit in the opinion of the treating physician. Patients who continue to receive study treatment after progression will continue with the on study requirements (as indicated by the study calendar "Cycle X" columns), **not** the off study requirements (as indicated by the study calendar column titled "F/U After Prog").
- b. Unacceptable toxicity.
- c. Women who become pregnant while participating in the study must discontinue study medication immediately. The pregnancy must be reported following procedures detailed in [Section 16.1](#).
- d. Treatment delay for any reason > 28 days from planned date of treatment.
- e. The patients may withdraw from the study at any time for any reason.

7.7 Discontinuation of Treatment

All reasons for discontinuation of treatment must be documented in the Off Treatment Notice.

7.8 Follow-Up Period

All patients will be followed until death or 3 years after registration, whichever occurs first.

8.0 TOXICITIES TO BE MONITORED AND DOSE MODIFICATIONS

8.1 NCI Common Terminology Criteria for Adverse Events

Two different versions of the NCI Common Terminology Criteria for Adverse Events (CTCAE) will be used on this study.

- a. Serious Adverse Event (SAE) reporting

The CTCAE (NCI Common Terminology Criteria for Adverse Events) Version 5.0 will be utilized **for SAE reporting only**. The CTCAE Version 5.0 can be downloaded from the CTEP home page (<https://ctep.cancer.gov>). All appropriate treatment areas should have access to a copy of the CTCAE Version 5.0.

b. Routine toxicity reporting

This study will utilize the CTCAE (NCI Common Terminology Criteria for Adverse Events) Version 4.0 for routine toxicity reporting. A copy of the CTCAE Version 4.0 can be downloaded from the CTEP home page (<https://ctep.cancer.gov>). All appropriate treatment areas should have access to a copy of the CTCAE Version 4.0.

8.2 General Dose Modification Guidelines

- a. Missed doses are to be omitted rather than made up.
- b. If multiple toxicities are experienced, dose modifications will be based on the toxicity requiring the largest dose reduction.
- c. Reductions are based on the dose given in the preceding cycle and are based on toxicities observed since the prior toxicity evaluation.
- d. If treatment is held > 28 days due to any reason, patient must be removed from protocol treatment.

8.3 Dose Modifications

a. Dose Modifications for Afatinib Plus Cetuximab (Arm 1)

Drug	Level 0	Level -1	Level -2	Level -3	Level -4
Afatinib	40 mg	30 mg	30 mg	30 mg	20 mg
Cetuximab	500 mg/m ²	375 mg/m ²	250 mg/m ²	Discontinue	--

Note: Once a dose reduction is applied, the reduced dose is maintained unless further dose reduction is needed.

For patients with CTCAE grade ≥ 3 drug related hypomagnesemia, only cetuximab dose should be reduced; there is no need to reduce the afatinib dose.

b. Dose Modifications for Afatinib Alone (Arm 2)

Drug	Level 0	Level -1	Level -2
Afatinib	40 mg	30 mg	20 mg

Note: Once a dose reduction is applied, the reduced dose is maintained unless further dose reduction is needed.

c. Hypersensitivity Reaction

In each case of hypersensitivity reaction, the investigator should institute treatment measures according to the best available medical practice. Based on previous experience with cetuximab hypersensitivity reactions, the following treatment guidelines may be applicable:

Toxicity Grade	Cetuximab modification
1	Decrease cetuximab infusion rate by 50% and monitor closely for any worsening.
2	Stop cetuximab infusion. Administer bronchodilators, oxygen, etc. as medically indicated. Resume infusion at 50% of previous rate after allergic/hypersensitivity reaction has resolved or decreased to Grade 1 in severity. Monitor closely for any worsening.
3 or 4	Stop cetuximab infusion immediately and disconnect infusion tubing from patient. Administer epinephrine, bronchodilators, antihistamines, glucocorticoids, intravenous fluids, vasopressor agents, oxygen, etc. as medically necessary. Discontinue all further cetuximab treatment.*

* Patients with CTCAE Grade ≥ 3 allergic reaction/hypersensitivity which can clearly be attributed to cetuximab will result in the permanent discontinuation of that drug only, with continuation of afatinib if deemed by the investigator that patient derived clinical benefit from continuation of afatinib.

d. Hypomagnesemia

Toxicity Grade	Cetuximab modification
1	Magnesium chloride starting at 2 tablets PO three times a day, titrating up to 4 tablets PO three times a day as needed. Treating physician may also consider weekly magnesium monitoring without replacement for Grade I hypomagnesemia in asymptomatic patients without cardiac history or cardiac risks.
2	Weekly intravenous replacement with magnesium sulfate 4 g.
3 or 4	Magnesium sulfate 6 to 10 g IV twice weekly, dependent on the patient. An initial strategy of IV replacement and every-other-day serum magnesium monitoring is helpful to guide the frequency of replacement until a steady state is reached. In a patient with normal renal function, start amiloride 5 mg PO daily and titrate up to 10 mg PO daily. Afatinib may be continued. Cetuximab should be held until recovery to Grade 2 or less. Upon recovery, resume cetuximab at next reduced dose level (afatinib dose does not need to be reduced). If \geq Grade 3 hypomagnesemia does not resolve to \leq Grade 2 within 28 days of stopping cetuximab and despite optimal supportive care, discontinue cetuximab.

e. Diarrhea

Close monitoring and proactive management of diarrhea is essential for successful treatment of patients with afatinib with or without cetuximab. Early and appropriate intervention can prevent the development of more severe diarrhea. In most cases, loperamide controls diarrhea caused by afatinib. Loperamide should be available at the start of therapy and kept with the patient at all times; it is therefore advisable that patients be given a prescription at the time of initiating

treatment with afatinib. Patients should be instructed to take two 2 mg loperamide tablets after the first episode of diarrhea, followed by one 2 mg tablet with every loose bowel movement, up to a maximum daily dose of 10 tablets (20 mg). In patients who have persistent diarrhea despite loperamide, a step-wise increase in anti-diarrheal therapy should be employed. Diphenoxylate/atropine (Lomotil) can be added (recommended dose of two 5 mg tablets up to 4 times daily, for a maximum daily dose of 20 mg) as can tincture of opium (recommended dose of 6 mg [or 10 mg/mL] up to 4 times daily, for a maximum daily dose of 24 mg [or 40 mg/mL]).

Toxicity Grade	Modification
1	Two 2 mg loperamide tablets should be taken immediately, followed by one 2 mg tablet with every loose bowel movement, up to a maximum daily dose of 10 tablets (20 mg). Add other anti-diarrheal agents as described above if necessary.
2	As with Grade 1, and appropriate rehydration (1.5 L/m ² /day plus equivalent of actual fluid loss) and electrolyte replacement.
2 lasting \geq 2 days	May be treated in manner similar to Grade 2 diarrhea. Treatment must be stopped until recovery to \leq Grade 1. Upon recovery, treatment should be resumed at next reduced dose level. If despite optimal supportive care and a treatment pause diarrhea does not resolve to Grade \leq 1 within 28 days of stopping treatment and despite optimal supportive care, discontinue protocol treatment.
3 or 4	May be treated in manner similar to Grade 2 diarrhea. Treatment must be paused until resolution to \leq Grade 1. Upon recovery, treatment should be resumed at next reduced dose level. If despite optimal supportive care and a treatment pause diarrhea does not resolve to Grade \leq 1 within 28 days of stopping treatment and despite optimal supportive care, discontinue protocol treatment.

f. Nausea and Vomiting

Toxicity Grade	Modification
Nausea 1 & Vomiting 0	Antiemetic treatment*, if deemed necessary by treating physician.
Nausea 2 & Vomiting 0 or Nausea 0-2 & Vomiting 1-2	Antiemetic treatment*. Hold study treatment if Grade 2 vomiting or Grade 2 nausea persists for 7 or more consecutive days despite optimal supportive care. Resume treatment at next reduced dose level when recovered to \leq Grade 1.
Vomiting 3 or 4 or Nausea 3 or 4	Antiemetic treatment*. Hold study treatment until recovery to \leq Grade 1 or baseline. Resume treatment at next reduced dose level when recovered to \leq Grade 1. If \geq Grade 3 nausea or vomiting does not resolve to \leq Grade 1 within 28 days of stopping treatment and despite optimal supportive care, discontinue protocol treatment.

* Antiemetic treatment should follow the recommendations given in the Consensus Statement of the Antiemetic Subcommittee of the Multinational Association of Supportive Care in Cancer (MASCC): Prevention of chemotherapy- and radiotherapy-induced emesis: Results of the Perugia Consensus Conference (R06-0986).

g. Rash, Acne, Paronychia

A proactive and early approach to management of rash is crucial. Rash can be managed by a variety of treatment options to relieve symptoms and to reduce the rash.

1. General/Prevention

- a. Patients should be educated on the importance of taking afatinib on an empty stomach.
- b. Hypoallergenic moisturizing creams, ointments and emollients should be used once or twice daily to prevent and alleviate skin dryness. Avoid topical acne medications. Use of gentle soaps (e.g. Dove unscented soap, Cetaphil cleansing lotion) and gentle shampoos.
- c. Patients should be cautioned about sun exposure, which can make the rash worse. Hypoallergenic sunscreen with a high SPF (at least SPF30, PABA free, UVA/UVB protection), preferably broad spectrum protection and/or physical blockers containing zinc oxide or titanium dioxide, should be applied to sun-exposed areas every two hours while in the sun (including exposure through windows). Protective clothing for sun protection and wearing a hat and sunglasses should be recommended.

- d. To prevent paronychia, patients should keep their hands dry and out of water whenever possible. They should avoid friction and pressure on the nail fold as well as picking or manipulating the nail. Trimming cuticles is discouraged as it increases risk for infection. Topical application of petrolatum around the nails is recommended.
- e. The use of prophylactic oral antibiotics (e.g. doxycycline 100 mg twice daily or minocycline 100 mg twice daily) has been shown to be effective in preventing or reducing the severity of skin toxicity associated with EGFR inhibitors. The prophylactic use of these agents can be considered for individual patients.

2. Management

Toxicity Grade	Management
1	Mild rash may not need treatment. However, if treatment is considered necessary, topical hydrocortisone (1% or 2.5%) cream and/or clindamycin 1% lotion applied twice daily can be used.
2	
Relief from major symptoms should be achieved by a combination of therapies including: systemic antibiotics (e.g. doxycycline 100 mg twice daily or minocycline 100 mg twice daily), topical treatment (e.g. for extremities and trunk use topical clobetasol 0.05% twice daily for up to two weeks; for face use hydrocortisone valerate 0.2% twice daily for up to two weeks or pimecrolimus 1% cream twice daily; for pustules use clindamycin 1% twice daily), antihistamines (e.g. diphenhydramine, etc), or oral corticosteroids at treating physician's discretion.
 
Systemic and topical treatment should be initiated at the start of Grade 2 rash and continued until improvement or resolution to \leq Grade 1. If Grade 2 rash persists for \geq 7 days despite treatment and is poorly tolerated by patient, treatment may be held for up to 28 days. Resume treatment at next reduced dose level when recovered to \leq Grade 1. If \geq intolerable Grade 2 rash does not resolve to \leq Grade 1 within 28 days of stopping treatment and despite optimal supportive care, discontinue protocol treatment.

3 or 4	May be treated in manner similar to Grade 2 rash. Additionally, treatment should be paused until resolution to \leq Grade 1. Resume treatment at next reduced dose level when recovered to \leq Grade 1. If \geq Grade 3 rash does not resolve to \leq Grade 1 within 28 days of stopping treatment and despite optimal supportive care, discontinue protocol treatment.

3. Management of paronychia is based on anecdotal evidence. Warm soaks and/or topical application for hydrocortisone 2.5% cream is recommended for symptomatic relief. Topical antibiotics (e.g. Burow's solution or aluminum acetate soaks, 4% thymol in alcohol, silver nitrate application) or systemic antibiotics may also be recommended. Patients may try liquid cyanoacrylates (e.g., Band-Aid® Liquid Bandage) to relieve pain and promote healing of fissures.

h. Mucositis, Stomatitis

Treatment is supportive and aimed at symptom control. Recommendations are summarized in the table below. Avoidance of agents containing iodine, thyme derivatives and prolonged use of hydrogen peroxide can be helpful. Dietary maneuvers such as promotion of soft, non-irritating foods like ice-creams, mashed/cooked vegetables, potatoes and avoidance of spicy, acidic or irritating foods such as peppers, curries, nuts and alcohol is also recommended. If the patient is unable to swallow foods or liquids, parenteral fluid and/or nutritional support may be needed.

Toxicity Grade	Modification
1	Oral rinses with agents such as non-alcoholic mouth wash, normal saline, diluted salt and baking soda solution.
2	Addition of topical analgesic mouth treatments, topical corticosteroids (clobetasol 0.05% gel), antiviral therapy if herpetic infection confirmed, antifungal therapy preferably topical on a case by case basis.
3 or 4	Same management as for Grade 2. Institute additional symptomatic therapy (topical or systemic) as clinically indicated. Additionally, treatment should be paused until resolution to \leq Grade 1. Resume treatment at next reduced dose level when recovered to \leq Grade 1. If \geq Grade 3 mucositis/stomatitis does not resolve to \leq Grade 1 within 28 days of stopping treatment and despite optimal supportive care, discontinue protocol treatment.

i. Pulmonary

Toxicity Grade	Modification
3 or 4	Hold all protocol treatment. If interstitial lung disease (ILD) is confirmed or strongly suspected, discontinue protocol treatment and treat appropriately. If an alternative diagnosis is made, protocol treatment can be resumed.

j. Hepatic

Toxicity Grade	Modification
SGOT or SGPT Grade 0-1 And Bilirubin Grade 0-2	No change
SGOT or SGPT Grade 2-4 Or Bilirubin Grade 3-4	Hold all protocol treatment until resolution to \leq Grade 1 or back to baseline values. Resume treatment at one reduced dose level when recovered. If toxicity does not resolve to \leq Grade 1 or baseline within 28 days of stopping treatment, discontinue protocol treatment.
SGOT or SGPT Grade 2-4 And Concomitant Bilirubin $> 2 \times$ IULN	Discontinue protocol treatment.

k. Other toxicity: For any other medically concerning toxicity \geq Grade 2, consider holding treatment until toxicity resolves to \leq Grade 1 and reduce dose by one dose level upon resuming treatment. If toxicity does not resolve to \leq Grade 1 within 28 days of stopping treatment and despite optimal supportive care, discontinue protocol treatment. For any medically concerning event \geq Grade 2, please contact the Study Chairs as needed.

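### Section 8.3e: the optional diphenoxylate/atropine schedule multiplies out to 40 mg/day, twice the 20 mg/day maximum in the same sentence

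*Combined protocol and SAP*

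**What the plan says.** Section 8.3e gives a step-wise scheme for diarrhea, used in both arms. Loperamide comes first: "Patients should be instructed to take two 2 mg loperamide tablets after the first episode of diarrhea", then one tablet per loose stool, "up to a maximum daily dose of 10 tablets (20 mg").

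If diarrhea persists, two further drugs may be used. "Diphenoxylate/atropine (Lomotil) can be added", at a "recommended dose of two 5 mg tablets up to 4 times daily, for a maximum daily dose of 20 mg". Tincture of opium is the other option, at a "recommended dose of 6 mg [or 10 mg/mL] up to 4 times daily, for a maximum daily dose of 24 mg [or 40 mg/mL"].

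The grade table that follows relies on this text. The Grade 1 row says "Add other anti-diarrheal agents as described above if necessary", and the Grade 2 row builds on Grade 1. For Grade 2 lasting two days or more, and for Grade 3 or 4, the entry begins "May be treated in manner similar to Grade 2 diarrhea".

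The only other anti-diarrheal regimen is the prophylaxis example in Section 7.4a, which concerns loperamide alone: "Loperamide 4 mg with the first dose of afatinib, followed by 2 mg every 4 hours for the first 3 days". No other section gives a dose or tablet strength for diphenoxylate/atropine.

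**The concern.** The sentence states a dose, a frequency and a daily maximum for one drug, and the three do not agree. Sites could prescribe up to 20 mg/day or up to 40 mg/day and each cite the same line.

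This is an operative instruction on an expected toxicity. In the Phase Ib/II trial of the combination (Section 2.0, Table 1), 71 of 100 patients had diarrhea, 7 of them at Grade 3 or higher. The patients affected by the sentence are those whose diarrhea has not responded to loperamide. What is at stake is consistent supportive-care dosing in that group.

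**Working it through.** **Inputs, all from Section 8.3e**

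- Diphenoxylate/atropine: 2 tablets per dose, 5 mg per tablet, up to 4 doses per day, stated maximum 20 mg/day.
- Tincture of opium: 6 mg per dose, up to 4 doses per day, stated maximum 24 mg/day.

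**Step 1. Does the stated maximum follow from the schedule?**

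Daily total = tablets per dose x mg per tablet x doses per day.

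- Per dose: 2 x 5 = 10 mg.
- Full schedule: 10 x 4 = 40 mg/day.
- Ratio to the stated maximum: 40 / 20 = 2.

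The printed 20 mg is not reproduced.

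**Step 2. Where does the schedule cross the maximum?**

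| Doses per day | Daily total | Relative to 20 mg |
|---|---|---|
| 2 | 20 mg | at the maximum |
| 3 | 30 mg | 1.5 times |
| 4 | 40 mg | 2 times |

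In tablets, the full schedule is 40 / 5 = 8 per day and the maximum is 20 / 5 = 4 per day.

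**Step 3. How does the parallel entry behave?**

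Opium has the same structure: dose, frequency, maximum. There 6 x 4 = 24 mg, which equals its stated maximum. This suggests that the maximum in such an entry is meant as the product of dose and frequency.

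**Step 4. Could the strength be a total per dose?**

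The loperamide text names two 2 mg tablets and equates 10 tablets with 20 mg (10 x 2 = 20), so strength there is per tablet. Nothing signals a different meaning for the diphenoxylate/atropine tablets.

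**Step 5. Which number is wrong?**

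Any one of four single changes restores agreement:

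- tablets per dose: 20 / (5 x 4) = 1;
- tablet strength: 20 / (2 x 4) = 2.5 mg;
- frequency: 20 / (2 x 5) = 2 per day;
- maximum: 2 x 5 x 4 = 40 mg.

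The documents give no basis for choosing among them.

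**Step 6. The opium brackets**

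The milligram doses agree, but the bracketed alternatives are in mg/mL. They run from 10 to 40 as if multiplied by the four doses (10 x 4 = 40). A concentration does not accumulate over doses and cannot be a daily maximum. This is a separate point about units and does not bear on Steps 1 to 5.

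**The case against.** The strongest reply is that the sentence can be followed as printed. The frequency is a ceiling, the daily maximum is a second ceiling, and the lower one binds. A site giving two 10 mg doses meets both, and exceeding 20 mg means passing a limit stated in the same line. Much of this stands, and it is why the point is minor. It does not remove the contradiction: on that reading the third and fourth permitted doses can never be given at the recommended dose, and the opium entry indicates that the maximum was meant to be the product.

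A reader might cite loperamide as a second entry whose maximum agrees with its schedule. It is not one. Ten 2 mg tablets making 20 mg only converts tablets to milligrams. Loperamide is taken per loose stool with no fixed frequency, so its cap does the limiting, which if anything favors the reading that the cap governs. Only opium tests dose times frequency against a maximum.

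It is also true that the consequences are limited. The drug is an optional add-on. Section 16.1e names only afatinib and cetuximab as investigational agents. The rules in Section 8.3e for pausing, reducing and stopping study treatment do not depend on this drug. The appendix list in Section 18.0 is marked closed effective 04/23/2018; if that means closure to accrual, a correction reaches only patients still on treatment. However, the adverse-event list in Section 3.1 is dated June 15, 2020, so the document was still being updated, and under Section 7.2 treatment continues until a removal criterion is met.

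**Conclusion.** The sentence is wrong as written. Its full schedule gives 40 mg/day against a stated maximum of 20 mg/day, a factor of 2, with the maximum reached after two of four permitted doses. This rests only on the printed numbers and on reading the strength as per tablet, as the loperamide text does.

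Two stronger readings are tempting, and the documents support neither:

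- A reader might infer that 20 mg is the correct figure and the per-dose amount is the error. Four different repairs fit, including a maximum of 40 mg, and nothing in the documents selects one.
- A reader might infer that patients are being overdosed or harmed. No grade requires the drug, the printed maximum limits exposure if followed, and the documents do not say what 40 mg/day would do.

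This is a minor supportive-care dosing correction, worth making because it is certain and cheap. Study-drug rules, sample size, power and alpha are unaffected.

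**What to change.** Have the sponsor's pharmacist confirm the intended tablet strength, tablets per dose, frequency and daily maximum, and rewrite the sentence in Section 8.3e so that they agree.

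Until that is settled, state that the lower printed limit of 20 mg/day governs. Interim wording could be 5 mg in total per dose up to four times daily (5 x 4 = 20 mg), or two 5 mg tablets no more than twice daily (10 x 2 = 20 mg). This is a precaution pending confirmation and does not decide that 20 mg is the right figure.

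In the same edit, have the pharmacist clarify what the bracketed opium values are meant to convey, since mg/mL is a strength and cannot state a dose or a daily maximum.

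Notify sites that still have patients on treatment.

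Cost: one sentence and a site memo. No design or analysis change.
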